### List of End of Text Listings:

Output	Title
Section 16.2.1 – Disposition	
Listing 16.2.1.1	Subject Disposition
Listing 16.2.1.2	Eligibility Criteria
Section 16.2.2 – Protocol Deviations	
Listing 16.2.2	Important Protocol Deviations
Section 16.2.3 – Excluded Subjects	
Listing 16.2.3	Analysis Populations
Section 16.2.4 – Demographics and Baseline Characteristics	
Listing 16.2.4.1	Subject Demographics
Listing 16.2.4.2	Medical History
Listing 16.2.4.3	Prior and Concomitant Medications
Section 16.2.5 – Compliance	
Listing 16.2.5.1	Study Drug Administration
Listing 16.2.5.2	Meal Administration
Section 16.2.6 – Response Data	
Listing 16.2.6.1	Plasma Concentrations
Listing 16.2.6.2	Plasma Pharmacokinetic Parameters
Listing 16.2.6.3	Urine Pharmacokinetic Parameters
Section 16.2.7 – Adverse Events Data	
Listing 16.2.7.1	Adverse Events
Listing 16.2.7.2	Adverse Events Leading to Study Drug Discontinuation
Section 16.2.8 – Laboratory Data	
Listing 16.2.8.1	Clinical Laboratory Results – Cardiac Markers
Listing 16.2.8.2	Clinical Laboratory Results – Chemistry
Listing 16.2.8.3	Clinical Laboratory Results – Coagulation
Listing 16.2.8.4	Clinical Laboratory Results – Hematology
Listing 16.2.8.5	Clinical Laboratory Results – Urinalysis
Listing 16.2.8.6	Clinical Laboratory Results – Serology
Listing 16.2.8.7	Clinical Laboratory Results – Pregnancy and FSH
Listing 16.2.8.8	Clinical Laboratory Results – Urine Drug and Alcohol Screen
Section 16.2.9-10 – Other Safety Data	

- Listing 16.2.9 Vital Signs
- Listing 16.2.10 12-Lead Electrocardiogram Results
- Listing 16.2.11 Cardiac Telemetry Results
- Listing 16.2.12 Echocardiogram Results
- Listing 16.2.13 Physical Examination Findings

**Other Appendix Outputs:**

Output	Title
Appendix 16.1.9.2	Statistical Appendices

## Appendix 4: Shells for Post-Text Tables, Figures and Listings

Shells are provided in a separate document.

## Appendix 5: Toxicity Table – Modified DMID Adult toxicity Table, 2014

Clinical Adverse Events			
VITAL SIGNS	Mild (Grade 1)	Moderate (Grade 2)	Severe (Grade 3)
Fever (°C) **	38.0 – 38.4	38.5 – 38.9	≥39.0
(°F) **	100.4 – 101.1	101.2 – 102.0	>102.0
** Oral temperature; no recent hot or cold beverages or smoking. A protocol should select either °C or °F for inclusion.			
Tachycardia - beats per minute	101 – 115	116 – 130	> 130 or ventricular dysrhythmias
Bradycardia - beats per minute	50 – 54 or 45-50 bpm if baseline <60 bpm	45 – 49 or 40-44 if baseline <60bpm	< 45 or <40bpm if baseline <60bpm
Hypertension# (systolic)- mm Hg	141-150	151-160	> 160
Hypertension# (diastolic) - mm Hg	91-95	96-100	> 100
# Assuming supine position, 10 min at rest conditions, not sleeping subjects, measurements on the same arm and several concordant results.			

Hypotension (systolic) - mm Hg	85-89	80-84	< 80
Tachypnea – breaths per minute	23-25	26-30	>30
CARDIOVASCULAR	Grade 1	Grade 2	Grade 3
Arrhythmia		asymptomatic, transient signs, no Rx required	recurrent/persistent; symptomatic Rx required
QTcF interval prolonged (msec)	Asymptomatic, QTcF >450-480 msec	Asymptomatic, QTcF >480-500 msec OR increase in interval 30-60 msec from baseline	Asymptomatic, QTcF >500 msec OR increase in interval >60 msec from baseline
Hemorrhage, Blood Loss	Estimated blood loss ≤ 100 mL	Estimated blood loss > 100 mL, no transfusion required	Transfusion required
RESPIRATORY	Grade 1	Grade 2	Grade 3
Cough	Transient- no treatment	Persistent cough;	Interferes with daily activities
Bronchospasm, Acute	transient; no treatment; 71% - 80% FEV1 of peak flow	requires treatment; normalizes with bronchodilator; FEV1 60% - 70% (of peak flow)	no normalization with bronchodilator; FEV1 <60% of peak flow
Dyspnea	Does not interfere with usual and social activities	Interferes with usual and social activities, no treatment	Prevents daily and usual social activity or requires treatment
GASTROINTESTINAL	Grade 1	Grade 2	Grade 3
Nausea	No interference with activity	Some interference with activity	Prevents daily activities
Vomiting	No interference with activity or 1 - 2 episodes/24 hours	Some interference with activity or > 2 episodes/24 hours	Prevents daily activity or requires IV hydration

Diarrhea	2 - 3 loose or watery stools or < 400 gms/24 hours	4 - 5 loose or watery stools or 400 - 800 gms/24 hours	6 or more loose or watery stools or > 800gms/24 hours or requires IV hydration
SYSTEMIC	Mild (Grade 1)	Moderate (Grade 2)	Severe (Grade 3)
Allergic Reaction/Hypersensitivity	pruritus without rash	localized urticaria	generalized urticaria; angioedema or anaphylaxis
Headache	No interference with activity	Repeated use of non-narcotic pain reliever > 24 hours or some interference with activity	Significant; any use of narcotic pain reliever or prevents daily activity
Fatigue	No interference with activity	Some interference with activity	Significant; prevents daily activity
Myalgia	No interference with activity	Some interference with activity	Significant; prevents daily activity
All Other conditions	Mild (Grade 1)	Moderate (Grade 2)	Severe (Grade 3)
Illness or clinical adverse event (as defined according to applicable regulations)	Transient or mild symptoms; no limitation in activity; no intervention required. The AE does not interfere with the participant's normal functioning level. It may be an annoyance.	Symptom results in mild to moderate limitation in activity; no or minimal intervention required. The AE produces some impairment of functioning, but it is not hazardous to health. It is uncomfortable or an embarrassment.	Symptom results in significant limitation in activity; medical intervention may be required. The AE produces significant impairment of functioning or incapacitation.

Laboratory Adverse Events					
Blood, Serum, or Plasma *	Reference Range **		Mild (Grade 1)	Moderate (Grade 2)	Severe (Grade 3)
Sodium – Hyponatremia mEq/L	135-146 mmol/L		134 – <LLN	132 – 133	<132
Sodium – Hypernatremia mEq/L	135-146 mmol/L		>ULN – 147	148 – 149	>149
Potassium – Hyperkalemia mEq/L	3.5-5.3 mmol/L		>ULN – 5.4	5.5 – 5.6	>5.6
Potassium – Hypokalemia mEq/L	3.5-5.3 mmol/L		<LLN-3.4	<3.4 – 3.3	<3.3
Glucose – Hypoglycemia mg/dL	65-99 mg/dL		62 – 64	52 – 62	<52
Glucose – Hyperglycemia Fasting – mg/dL	65-99 mg/dL		>ULN - 100	101 – 110	>110
Glucose – Hyperglycemia Random – mg/dL	65-139 mg/dL		140 – 159	160 – 200	>200
Blood Urea Nitrogen mg/dL	7-25 mg/dL		26 – 29	30 – 34	>34
Creatinine (Male) – mg/dL	18Y-19Y	0.60-1.26 mg/dL	>ULN – 1.36	>1.36 – 1.56	>1.56
	20Y-49Y	0.60-1.35 mg/dL	>ULN – 1.45	>1.45 – 1.65	>1.65
	50Y-59Y	0.70-1.33 mg/dL	>ULN – 1.43	>1.43 – 1.63	>1.63
Creatinine (Female)- mg/dL	18Y-19Y	0.50-1.00 mg/dL	>ULN – 1.10	>1.10 – 1.30	>1.30
	20Y-49Y	0.50-1.10 mg/dL	>ULN – 1.20	>1.20 – 1.40	>1.40
	50Y-59Y	0.50-1.05 mg/dL	>ULN – 1.15	>1.15 – 1.35	>1.35
Calcium – hypocalcemia mg/dL (Male)	18Y-19Y	8.9-10.4 mg/dL	8.8 – <LLN	8.3 – 8.7	<8.3
	20Y-133Y	8.6-10.3 mg/dL	8.5 – <LLN	8.0 – 8.4	<8.0
Calcium – hypocalcemia mg/dL (Female)	18Y-19Y	8.9-10.4 mg/dL	8.8 – <LLN	8.3 – 8.7	<8.3
	20Y-49Y	8.6-10.2 mg/dL	8.5 – <LLN	8.0 – 8.4	<8.0
	50Y-133Y	8.6-10.4 mg/dL	8.5 – <LLN	8.0 – 8.4	<8.0
Calcium – hypercalcemia mg/dL (Male)	18Y-19Y	8.9-10.4 mg/dL	>ULN – 10.5	10.6 – 11.0	>11.0
	20Y-133Y	8.6-10.3 mg/dL	>ULN – 10.4	10.5 – 10.9	>10.9
Calcium – hypercalcemia mg/dL (Female)	18Y-19Y	8.9-10.4 mg/dL	>ULN – 10.5	10.6 – 10.9	>10.9
	20Y-49Y	8.6-10.2 mg/dL	>ULN – 10.3	10.4 – 10.7	>10.7
	50Y-133Y	8.6-10.4 mg/dL	>ULN – 10.5	10.6 – 10.9	>10.9

Magnesium – hypomagnesemia mg/dL	1.5-2.5 mg/dL		1.3 – 1.5	1.1 – 1.2	<1.1
Phosphorous – hypophosphatemia mg/dL	18Y-64Y	2.5-4.5 mg/dL	2.3 – <2.5	2.0 – < 2.2	<2.0
	65Y-133Y	2.1-4.3 mg/dL	1.9 – <2.1	1.6 – < 1.8	<1.6
CPK – U/L (male)	<196		196 – 1000	1001-1500	>1500
CPK – U/L (female)	<143		143 – 1000	1001-1500	>1500
Albumin – Hypoalbuminemia g/dL	3.6-5.1 g/dL		3.0 – 3.5	2.7 – 2.9	<2.7
Total Protein – Hypoproteinemia g/dL	18Y-19Y	6.3-8.2 g/dL	6.1 – 6.3	5.7 – 6.0	<5.7
	20Y-133Y	6.1-8.1 g/dL	5.9 – 6.1	5.5 – 5.8	<5.5
Alkaline phosphatase – U/L (Male)	18Y-19Y	48-230 U/L	230 – 340	341 – 460	>460
	20Y-133Y	40-115 U/L	115 – 225	226 – 345	>345
Alkaline phosphatase – U/L (Female)	18Y-19Y	47-176 U/L	176 – 286	287 – 406	>406
	20Y-49Y	33-115 U/L	115 – 225	226 – 345	>345
	50Y-133Y	33-130 U/L	130 – 240	241 – 360	>360
AST (Male) U/L	18Y-19Y	12-32 U/L	32 – 93	94 – 163	>163
	20Y-49Y	10-40 U/L	40 – 101	102 – 171	>171
	50Y-133Y	10-35 U/L	35 – 96	97 – 166	>166
AST (Female) U/L	18Y-19Y	12-32 U/L	32 – 93	94 – 163	>163
	20Y-44Y	10-30 U/L	30 – 91	92 – 161	>161
	45Y-133Y	10-35 U/L	35 – 96	97 – 166	>166
ALT (Male) U/L	18Y-19Y	8-46 U/L	46 – 101	102 – 171	>171
	20Y-133Y	9-46 U/L	46 – 101	102 – 171	>171
ALT (Female) U/L	18Y-19Y	5-32 U/L	32 – 87	88 – 157	>157
	20Y-133Y	6-29 U/L	29 – 84	85 – 154	>154
Bilirubin (serum total) mg/dL	18Y-19Y	0.2-1.1 mg/dL	1.2 – 1.9	2.0 - 2.4	>2.4
	20Y-133Y	0.2-1.2 mg/dL	1.3 – 2.0	2.1 – 2.5	>2.5
Bilirubin – when ALT ≥105 (Hy's law)			1.3 – 1.5	1.6 – 2.0	>2.0
Amylase- U/L	21 – 101 U/L		102 – 177	178 – 278	>278
Lipase- U/L	7 – 60 U/L		60 – 165	166 – 250	>250
Hemoglobin (Male) - g/dL	18Y	12.0-16.9 g/dL	11.5 – 12.0	10.5 – 11.9	<10.5
	19Y-133Y	13.2-17.1 g/dL	12.7 – 13.2	12.2 – 12.7	<12.2
Hemoglobin (Female) - g/dL	18Y	11.5-15.3 g/dL	11.0 – 11.5	9.5 – 10.9	<9.5
	19Y-133Y	11.7-15.5 g/dL	11.2 – 11.7	9.8 – 11.2	<9.8
WBC Increase - cell/mm3	18Y	4,500-13,000/uL	13,001 – 17,000	17,001 – 22,000	>22,000
	19Y-133Y	3,800-10,800/uL	10,801 – 14,800	14,801 – 19,800	>19,800
WBC Decrease - cell/mm3	18Y	4,500-13,000/uL	3,500 – 4,500	2,500 – 3,499	<2,500
	19Y-133Y	3,800-10,800/uL	2,800 – 3,800	1,800 – 2,799	<1,800

Lymphocytes Decrease - cell/mm 	18Y	1200-5200 cells/uL	950 – 1,200	700 – 949	<700
	19Y-133Y	850-3900 cells/uL	600 – 850	450 – 599	<450
Neutrophils Decrease - cell/mm 	18Y	1800-8000 cells/uL	1,300 – 1,799	1,049 – 1,299	<1,049
	19Y-133Y	1500-7800 cells/uL	1,000 – 1,499	750 – 999	<750
Eosinophils - cell/mm 	15-500 cells/uL		500 – 750	751 – 1600	>1600
Platelets Decreased - cell/mm 	140,000 – 400,000/ uL		130,000 – 140,000	110,000 – 129,999	<110,000
PT – seconds (prothrombin time)	9.0-11.5 seconds		> ULN-14.4	14.5 – 15.7	>15.7
PTT – seconds (partial thromboplastin time)	22-34 sec		>ULN-34.1	34.2– 42.0	>42.0
Fibrinogen increase - mg/dL	175-425 mg/dL		>ULN – 425	426 – 525	>525
Fibrinogen decrease - mg/dL	175-425 mg/dL		<LLN – 175	160 – 174	<160
Urine *			Mild (Grade 1)	Moderate (Grade 2)	Severe (Grade 3)
Protein			1+	2+	>2+
Glucose			1+	2+	>2+
Blood (microscopic) - red blood cells per high power field (rbc/hpf)			5-10	11-50	> 50 and/or gross blood
	* The laboratory values provided in the tables serve as guidelines and are dependent upon institutional normal parameters.				
	* Institutional normal reference ranges should be provided to demonstrate that they are appropriate.				
	** Reference ranges are from Quest Diagnostics. Any age range that is not specified is 18Y – 133Y				

### 3.1 Actions Taken/Con Meds Administered Related to Adverse Events:

Subject #	AE #	Medication	Dose/Unit	Route	Start Date	Stop Date	Prescribed for:

**4.0 Vital Signs Data (summary of clinically significant abnormal vital signs by subject # and time point taken):**

Subject #	Screening #	M/F	Age	Date	Time	Values	Grade
							N/A

\*There were no vital signs which met the criteria for halting dosing in Section 11.5.2 of the protocol.

**5.0 12-Lead ECG Data (summarize clinically significant abnormal changes by subject # and time point taken):** There were no clinically significant ECG findings, and no ECG parameters met the criteria for halting dosing stated in Section 11.5.2 of the protocol.

**6.0 Physical Examination Data (summarize clinically significant abnormal changes by subject # and time point performed):** There were no clinically significant physical exam findings noted.

**7.0 Subject Discontinuations:** No subjects were discontinued.

[figure not shown]

### 9.0 Investigator opinion about safety of IP based upon clinical tolerance of trial during reported period:

Internal review of all available safety data prior to the dose escalation call shows no concerns with proceeding to the next dose level.

### 2.0 Adverse Events

Subject #	AE #	Adverse Event	Date of Onset	Time of Onset	Date of Resolution	Time of Resolution	Severity	Relationship to IP

### 2.1 Adverse Event Comments (summarize findings from above table):

Subject #	AE #	Adverse Event	Comments

**3.1 Actions Taken/Con Meds Administered Related to Adverse Events:**

Subject #	AE #	Medication	Dose/Unit	Route	Start Date	Stop Date	Prescribed for:

**8.0 PK Summary (insert tables, appendices as allowed by sponsor, if available):**

Subjects in the table below have been anonymized with an alphabet code. Given the way the cohort dosing was staggered and that samples through only 24 hours post dosing were available for one subject in the cohort, only geometric mean data is presented in order to maintain the blind. If the subject received active, their half-life and clearance parameters are not included in the mean.

Additionally, the  $C_{max}$  for 3 subjects was greater than 10000 ng/mL (the upper limit of quantitation in the assay) and there was not time to re-assay prior to the dose escalation meeting. Therefore, it is possible that the AUC and  $C_{max}$  parameters are slightly underestimated. The anticipated geometric mean  $C_{max}$  for this cohort was approximately 10000-11000 ng/mL, so it is not anticipated that the  $C_{max}$  concentrations are much greater than 10000 ng/mL, or that the AUC parameters are significantly higher than calculated below.

[figure not shown]
No PK parameters met halting rules, and overall, the PK following a 10 mg/kg single dose administered by IV infusion was in line with anticipated exposure based on modeling and simulation and the exposure in Cohort 1 (5 mg/kg dose). Furthermore, the simulated exposure for the next two dose levels is not anticipated to exceed the PK stopping criteria in the protocol.

	T $\frac{1}{2}$ (h)	$C_{max}^*$ (ng/mL)	AUC 0-24h (ng.h/mL)	AUC 0-last (ng.h/mL)	AUC 0-inf (ng.h/mL)	%AUC extrap	Cl (mL/h/kg)	Vz (mL/kg)
Geomean	89.1	9240	20400	30200	32400	11.1	285	36600
%CV	21.6	10.6	12.8	14.1	20.9	41.5	14.2	35.4

\* 3 subjects had a  $C_{max}$  > 10000 ng/mL

The figure below shows the mean galidesivir concentration-time profiles for the first two cohorts of this study.

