- One or more subjects with a treatment-emergent QT interval corrected by Fridericia's formula ($QTcF$) > 480 ms (Grade 2 per the DMID scale) as determined from bedside ECGs (with repeat ECG). If this occurs, the SMC may consult with an independent cardiologist as needed. If it is deemed acceptable to restart the study following review of the data and discussion with an independent cardiologist, if needed, dosing may resume.
- One or more subjects experiences an increase in BP that requires acute treatment, or has a confirmed systolic BP > 160 mmHg, or a confirmed diastolic BP > 100 mmHg (Grade 3 per DMID scale). Confirmed BP changes require at least 2 measurements at least 2 hours apart, each measured after at least 5 minutes of supine rest.
- Anaphylactic reaction occurs in one subject.

- One or more subjects experience a similar Grade 3 treatment-emergent laboratory abnormality or AE that is suspected to be drug-related as determined by the investigator.
- One subject experiences an SAE.
- A cohort's median AUC₂₄ is $\geq 52,500$ ng.h/mL, equivalent to the NOAEL exposure in cynomolgus monkeys.

If any of the above criteria are met, escalation to the next planned dose cohort will not proceed until all available study data have been reviewed by the independent SMC, as per Section 11.5.3.

If, following review by the SMC (Section 11.5.3) it is deemed acceptable to restart the study, dosing will resume. All relevant data will be submitted to the regulatory authorities and IRB.

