12.3.1.4. Pharmacokinetic Analysis

Concentrations of galidesivir will be determined by validated plasma and urine assays and will be summarized by treatment and displayed in figures. Plasma PK parameters for each subject will be estimated over the sampling interval using noncompartmental analysis (Phoenix WinNonlin Version 7.0 or higher, Certara) and summarized by treatment group using descriptive statistics. The amount and percentage of galidesivir excreted in the urine will be assessed at all doses. If possible, data will be summarized by cohort and dose proportionality assessed.

The PK parameters that will be estimated for galidesivir are listed in [Table 9](#). Additional analyses may be conducted as appropriate.

Table 9: Pharmacokinetic Parameters

Pharmacokinetic Parameter	Definition
AUC _{inf}	Area under the concentration versus time curve extrapolated to infinite time, calculated as AUC _{last} + (C _{last} /λ _z)
AUC _t	Area under the concentration versus time curve from time zero to time “t”; may be denoted as AUC _{last} if the “t” is the last timepoint with a measurable concentration
% AUC _{exp}	Percentage of AUC extrapolated between AUC _{last} and AUC _{inf}
C _{last}	Last measurable concentration of drug
C _{max}	Maximum observed concentration of drug
t _{1/2}	Estimate of the terminal elimination half-life of the drug
CL	CL = Dose/AUC where “Dose” is the dose of the drug and AUC = AUC _{inf}
λ _z	Terminal elimination rate constant, estimate by linear regression of the terminal elimination phase of the concentration of drug versus time curve
V _z	Volume of distribution of the drug
T _{max}	Time to C _{max}
CL _r	Renal clearance of unchanged drug in a specific interval (CL _r [interval]) or cumulatively over all collection intervals
% Dose _{excreted}	Percentage of given dose excreted in the urine as unchanged drug

In all derivations of PK parameters, zero will be substituted for concentrations below the quantitation limit (BQL) of the assay. Samples that are BQL, but are between two samples with detectable concentrations will be excluded from PK analysis.

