### 7.2 Interim Analysis and Key Results

An interim PK report will be prepared by Biocryst for review by the DEC that will document the following PK findings for each dose cohort:

- Preliminary plasma PK parameters (through 24-hours post-dose) based upon nominal times: AUC;  $C_{max}$ ,  $T_{max}$ , terminal elimination half-life ( $t_{1/2}$ ; median, minimum, maximum, geometric mean, coefficient of variation [CV%])
- Predictions of  $C_{max}$  and AUC values for the next cohort, where relevant

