### 8.2 Acceptance of Data for Summarization

Programming of analysis datasets and TFLs may be ongoing during the data management of the study. However, programming of analysis datasets and TFLs will be completed and quality controlled (QC'd) after

database lock. Only quality-assured results released by the Safety Laboratory, Bioanalytical Laboratory, or other external data source will be used for the programming of analysis datasets and TFLs for the final report. Any data values requiring investigation or corrections that are identified while programming the analysis datasets and TFLs will be sent to the project Data Manager. If the issue affects the TFLs the Programmer or Statistician who identified the issue will follow it to resolution.

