### 9.0 Summary of Discussion at Dose Escalation Call:

Based upon safety measures, tolerance, and pharmacokinetic results, the dose of 10 mg/kg was well tolerated. The Safety Committee discussed data and agreed that data supports moving forward with dose escalation and with no change to the protocol.

**Current Dose Level:** 10 mg/kg

**Next Dose Level:** 15 mg/kg

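### The AUC24 safety stop in Protocol 11.5.2 can be applied before samples above the assay limit are quantified; a missed breach is unlikely, and two added sentences would close the gap

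*SAP*

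**What the plan says.** Protocol 11.5.2 (also the synopsis and 7.6.2) holds escalation for SMC review when a cohort's median AUC24 is at or above 52,500 ng.h/mL, described as "equivalent to the NOAEL exposure in cynomolgus monkeys". The input is an interim report containing, in the words of SAP 7.2, "Preliminary plasma PK parameters (through 24-hours post-dose) based upon nominal times", together with predictions for the next cohort.

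The assay-limit rules deal only with low values. Protocol 12.3.1.4 says "zero will be substituted for concentrations below the quantitation limit (BQL) of the assay", and SAP 16.1.1 and 16.2.2 also address only values below the limit. SAP 8.2 requires quality-assured laboratory results, but for data that "will be used for the programming of analysis datasets and TFLs for the final report", not for the interim report.

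The Cohort 2 (10 mg/kg) dose-escalation report appended to the SAP shows the gap in use. Its PK summary says that three subjects had Cmax above 10,000 ng/mL, the upper limit of the assay, that "there was not time to re-assay prior to the dose escalation meeting", and that AUC and Cmax might be slightly underestimated. The anticipated geometric mean Cmax "for this cohort was approximately 10000-11000 ng/mL", so values over the limit were foreseeable. The committee "agreed that data supports moving forward with dose escalation and with no change to the protocol".

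**The concern.** An over-limit sample that is not re-assayed can only pull AUC24 down. The error therefore runs one way: it can hide a breach of the stop but cannot create one. It also grows with dose, because more subjects and more samples near the end of infusion pass 10,000 ng/mL.

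At 20 mg/kg the projected exposure comes closest to the threshold. That is the top planned dose, and its subjects will already have been dosed when the rule is applied. What is at stake is a missed SMC referral and a low reading for the condition in Protocol 11.5.3 that exposure be below the NOAEL before cohorts are added. The same low values also feed the prediction for the next cohort.

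**Working it through.** **Inputs.** Threshold 52,500 (Protocol 11.5.2). Cohort 2 geometric means: Cmax 9,240, AUC24 20,400 with CV 12.8% (appended report, PK summary). Assay limit 10,000 (same place). Expected AUC24 at 20 mg/kg 47,000; at 5 mg/kg, Cmax about 3,000 and AUC24 about 10,000 (Protocol 4.4.3). Sampling at 0.5, 1, 1.25, 1.5 and 2 h (Protocol 11.2.1). Six active subjects per cohort.

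**Assumptions.** Over-limit values are entered as 10,000; the report does not say how they were entered. The Cmax row fits this: with three values at 10,000, the other three must have geometric mean 9,240²/10,000 = 8,538, which is plausible but not proof. The report gives geometric means only, so 20,400 stands in for the median.

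**1. The plan's own figure.** AUC24 of 20,400 cannot be rebuilt, because no subject-level concentrations are shown. The same table is consistent elsewhere: Vz = CL × t½ / ln 2 = 285 × 89.1 / 0.693 = 36,635, against 36,600 reported.

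**2. Was the Cohort 2 decision safe?** The margin is 52,500/20,400 = 2.57. Linear-trapezoid weights are 0.5 h for the 0.5 h sample, 0.375 h for 1 h and 0.25 h for 1.25 h, in total 1.125 h. If all three samples were truly 20,000 in every subject, the hidden area is 1.125 × 10,000 = 11,250, giving 31,650, or 60% of the threshold. The decision stands.

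**3. What would a true 52,500 read at 20 mg/kg?** Hand calculation, assuming the 0.5 h and 1.25 h samples are 75% and 70% of Cmax.

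| Profile | Cmax at AUC24 52,500 | Hidden area (1 h + 0.5 h + 1.25 h) | Reads |
|---|---|---|---|
| Cohort 2, Cmax 9,240 at 10 mg/kg | 23,779 | 5,167 + 3,917 + 1,661 = 10,746 | 41,754 |
| Cohort 2, Cmax 10,100 at 10 mg/kg | 25,993 | 5,997 + 4,747 + 2,049 = 12,793 | 39,707 |
| Protocol 4.4.3, Cmax/AUC24 = 12,000/47,000 | 13,403 | 1,276 + 26 + 0 = 1,302 | 51,198 |
| Protocol 4.4.3, Cmax/AUC24 = 3,000/10,000 | 15,750 | 2,156 + 906 + 256 = 3,319 | 49,181 |

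(12,000 is 4 × 3,000. Sums may differ by 1 through rounding.) Tri-exponential 1-hour infusion curves fitted to each profile, integrated by the linear-up/log-down rule with and without the cap, give about 37,000-43,000 for the Cohort 2 profile and 47,800-51,200 for the Protocol 4.4.3 profile. All of these are below the trigger.

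**4. How likely is a true breach?** Simulated median of six lognormal values, CV 12.8%, 4,000,000 cohorts per case:

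- Mean 40,800 (2 × 20,400): about 0.001%.
- Mean 47,000: 3.1%.

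Allowing for sampling error in Cohort 2's mean, the dose-proportional case rises to 0.5%. Reaching 52,500 from 20,400 over a doubling of dose needs a dose exponent of log2(52,500/20,400) = 1.36. The intramuscular study gives 1.08 (Day 1 AUCtau, ln(21,700/4,830)/ln 4) to 1.13 (AUCt, ln(27,100/518)/ln(10/0.3)).

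**The case against.** The strongest reply is that nothing went wrong. The report disclosed the shortfall, gave its direction and reasoned about its size. It also stated that "the simulated exposure for the next two dose levels is not anticipated to exceed the PK stopping criteria in the protocol". Other protections exist: 7.6.2 allows escalation to be modified on emerging PK, the clinical stopping criteria work independently, 7.1 sends each cohort's data to FDA, and cohorts beyond 20 mg/kg need an SMC recommendation and a protocol amendment. A bioanalytical plan, not supplied, might cover re-assay. All of this limits the harm, and none of it is disputed. It does not supply the missing rule. Whatever other plan existed, it did not secure re-assay before the Cohort 2 meeting, and a stop meant to check the simulations should not rely on them.

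Four stronger readings are tempting and are not supported:

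- *Escalation to 15 mg/kg was unsafe.* The 2.57-fold margin rules this out.
- *Cohorts 3 and 4 were judged on capped values.* The PK text for those cohorts is not available here, so their handling is unknown.
- *The stop is effectively disabled even for a large excess.* A true 60,000 would need exponent log2(60,000/20,400) = 1.56, and no document supports that.
- *Low readings would ease added cohorts through the proportionality condition in 11.5.3.* On the Cohort 2 profile a proportional 40,800 would read 33,000-35,700, an apparent exponent of 0.69-0.81. That would count against the condition. Only the NOAEL condition is biased towards permission.

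**Conclusion.** The gap is real and small. As written, the plan allows a safety comparison to be made on AUC24 values known to be biased downwards, and this happened once without consequence. Near the threshold at 20 mg/kg, capped values would leave a true breach unreferred on either profile. The chance that such a breach exists is about 0.001% on dose-proportional scaling from Cohort 2 and about 3% on the protocol's own projection.

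The size of the under-reading rests on the capping assumption and on which profile holds. The Cohort 2 ratio of Cmax to AUC24 (9,240/20,400 = 0.45) favours the larger bias, while the 3% rests on the pre-study projection, so the two should not be combined as if one source gave both. The absence of a rule and the direction of the bias rest on neither. This is a worthwhile, inexpensive improvement. It is not evidence of a wrong decision, and the final PK analyses are not affected.

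**What to change.** Add to Protocol 11.5.2, with SAP 7.2 to match:

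> Samples above the upper limit of quantitation will be diluted and re-assayed before median AUC24 is compared with 52,500 ng.h/mL or used to predict exposure in the next cohort. If re-assay is not complete, the DEC will be shown a conservative upper bound for the median AUC24, and escalation may proceed without SMC review only if that upper bound is below 52,500.

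The method for the bound should be fixed in advance, for example by setting each over-limit sample to twice the anticipated Cmax. At 10 mg/kg that is at most 22,000. Applied to the 0.5, 1 and 1.25 h samples of every subject it gives 20,400 + 1.125 × 12,000 = 33,900, so Cohort 2 would still have escalated on schedule.

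The cost is one extra bioanalytical run and possibly a short delay when the margin is narrow. No additional blood or subjects are needed.
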